PART B STUDY DESCRIPTION

TITLE OF PROTOCOL	Development of a two-stage cervical cancer screening algorithm for Botswana
Principal Investigator	[name]

B1. PURPOSE OF PROTOCOL

Cervical cancer screening programs vary across settings and there is no clear guidance for effective screening programs for HIV-positive women. Evaluating the performance of algorithms that include human papillomavirus (HPV) DNA testing as first stage screening in high HIV prevalence settings like Botswana is essential for establishing an evidence-based strategy for cervical cancer screening in HIV-positive women. The proposed study seeks to evaluate sensitivity, specificity, and positive predictive value (PPV) of two different two-stage cervical cancer screening algorithms for HIV-positive women in Botswana: HPV followed by Papanicolaou (Pap) smear, and HPV followed by visual inspection with acetic acid (VIA). The specific aims are:

1. To determine the sensitivity, specificity, and PPV of a two-stage screening algorithm that utilizes HPV testing followed by Pap smear for the detection of high-grade cervical dysplasia, using colposcopy with histology as the gold standard.
2. To determine the sensitivity, specificity, and PPV of a two-stage screening algorithm that utilizes HPV testing followed by VIA for the detection of high-grade cervical dysplasia, using colposcopy with histology as the gold standard.

B2. SIGNIFICANCE AND BACKGROUND FOR THE STUDY

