Cervical cancer screening strategies are most effective when based on local evidence and tailored to the population and resource infrastructure.^{xxiii,xxiv} Available screening tests include HPV testing, cytology [liquid-based or Pap smear], and VIA. HPV testing has a high sensitivity (93-100%) and specificity (80-90%), but low PPV (12-23%) for pre-invasive disease.^{xxv,xxvi,xxvii,xxviii} Cytology is operator dependent, with variable sensitivity (43-94%) and specificity (78-98%), but PPV of up to 90%.^{xxix,xxx,xxxI} VIA sensitivity (17-100%) and specificity (8-95%) also are variable, and in resource-poor settings without HPV testing or histopathology can reduce cervical cancer mortality.^{xxxii,xxxiii,xxxiv} There is increasing evidence that primary HPV testing is the most effective screening strategy.^{xxxv,xxxvi,xxxvii,xxxviii} Primary testing with HPV alone, followed by treatment, creates a high likelihood of overtreatment and harm to women who desire future fertility. In addition, primary HPV testing followed by colposcopy is not feasible in settings like Botswana where there are an insufficient number of trained colposcopists. To address these two issues, two-stage screening strategies, consisting of HPV testing followed by either cytology or VIA, have been advocated.^{xxxix,xl,xli} HPV testing followed by cytology results in increased sensitivity and specificity.^{xlii} In a single study from Cameroon in a population with a high prevalence

of HIV (14.2%), HPV testing followed by Pap smear has been shown to have superior sensitivity and specificity compared to HPV testing followed by VIA.^{xliii}

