The proposed study will enroll 300 women for HPV testing in order to evaluate 81 HPV-positive women (see Sample Size calculations below). The first 100 enrollments will be nested within an existing cross-sectional pilot study designed to determine the uptake, acceptability, and feasibility of testing women for HPV using self-collected samples. The goal of this 100-person pilot study is to inform the future scale-up of primary HPV screening, by answering the question of whether self-collected swabs are as good as provider-collected swabs. These 100 participants will self-collect a vaginal specimen and undergo a concomitant provider-collected specimen for HPV testing; a provider-collected approach will be used for the subsequent 200 women who enroll for this proposed study. Co-enrollment with the existing pilot study leverages the existing study and facilitates use of the same staff and resources to ultimately accrue 300 women at minimal cost.

Research question

Which two-stage cervical cancer screening algorithm is more effective for HIV-positive women in Botswana: HPV followed by Papanicolaou (Pap) smear or HPV followed by visual inspection with acetic acid (VIA)?

Study Procedures

[figure not shown]
For all 300 participants, HPV testing will be performed with either the commercially-available Cepheid Xpert[®] HPV Assay or the commercially-available Roche Cobas[®] HPV Assay for provider- and participant-collected samples, as per the protocol of the HPV pilot study. The pilot study currently utilizes a Cepheid GeneXpert machine on loan from the National Health Laboratory (NHL), and the duration of its availability is unknown. Should the GeneXpert machine become unavailable, the Roche Cobas[®] machine at the NHL will be used for HPV testing. After the HPV pilot study ends, the remaining 200 participants will be enrolled and screened in a similar manner using a provider-collected approach. This study introduces Pap smear collection for all participants at the time of provider-collected HPV specimen. Pap smear will be prepared using standard technique at the site of collection.

Participants who test HPV-negative will have their Pap smear sent to the NHL for staining and pathologist evaluation. If the Pap smear is abnormal, they will be referred to colposcopy per current Botswana Cervical Cancer guidelines.

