Per the protocol of the HPV pilot study, participants who test HPV-positive will be asked to return for colposcopy and will undergo further diagnosis and treatment for cervical cancer per national guidelines. Participants who have positive HPV screening will have: 1) Pap smear sent to the NHL for review and 2) VIA at the colposcopy visit but performed prior to colposcopy. At the second visit - prior to the colposcopy - a trained nurse will conduct VIA using the Botswana standard protocol. After application of acetic acid to the cervix, the nurse will record visual results as positive or negative. If VIA is positive based on assessment of the lesion(s), the nurse will record a recommendation for either cryotherapy or loop electrosurgical excision procedure (LEEP). Since all of these HPV-positive participants will undergo colposcopy, the participants will not be informed of the VIA results, as neither cryotherapy nor LEEP will be administered based on the VIA results. Rather, the participants will proceed to colposcopy as planned in the HPV pilot study (and as will be continued for the women participating only in this study) and results of colposcopy will determine further diagnosis and treatment. This design leverages the existing HPV pilot study and enables us to assess the utility of both HPV/Pap and HPV/VIA two-stage algorithms while providing the highest-quality follow-up to cervical cancer screening abnormalities in Botswana.

Participants will thus have a total of two study-related encounters if they are HPV positive - one for initial screening and the one for the second-stage of screening and colposcopy. Participants who are HPV negative will only have the one study-related initial screening visit. Participants will also be asked if they want to be contacted in the future regarding participation in future research related to cervical screening and treatment. If the participant agrees, they will check yes for future contact in the consent form.

Cervical cancer screening study flow

The study site is only in Botswana; however, statistical analysis will be done with support from staff at BIDMC.

A detailed data monitoring and safety plan has been developed. All adverse events will be reviewed by the PI and co-investigators. All serious adverse events will be reviewed by the PI, co-investigators and a designated safety monitor, [name].

B. Statistical Considerations

Sample Size

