The goal of a two-stage algorithm is to increase PPV while maintaining sensitivity and specificity, and thus reduce overtreatment. Sample size assumptions were based on preliminary data, existing literature, and patient behavior regarding clinical follow-up. Among the first 25 women recruited in the parent study, the incidence of HPV-positivity was 30%. In a population with relatively high HIV prevalence, the PPV of an HPV-positive test for high-grade cervical dysplasia was 24%.^{xlvi} Our sample size calculation was targeted to detect an improvement in PPV of 25% between HPV testing alone and either two-stage algorithm (a PPV of 49% for the two-stage algorithms). Assuming a two-sided test and an alpha of 0.05, a sample size of 81 participants will yield over 80% power to detect the specified difference. Clients receiving care at the Infectious Disease Care Clinic (IDCC) tend to return for clinical follow-up appointments, because they come to IDCC each month to obtain their free anti-retroviral medications. Clients seeking care at the gynecology outpatient clinic may be less integrated into routine care. Thus, we anticipate that approximately 10% of HPV-positive participants will not return for colposcopy. The proposed study will aim to enroll 300 participants to yield 90 who are HPV positive 81 of whom we expect to return for colposcopy.

Data analysis

All data will be analyzed using SAS 9.4 (Cary, NC) at Beth Israel Deaconess Medical Center. Descriptive statistics will be presented as mean with standard deviation, median with interquartile range, or proportion, based on data type and distribution. Data will be compared using the appropriate parametric or non-parametric test for continuous variables and Chi-square or Fisher's exact test for categorical variables. All tests will be two-sided and a p-value <0.05 will be considered statistically significant.

We will calculate sensitivity, specificity and PPV of HPV/Pap smear and HPV/VIA to detect high-grade cervical dysplasia amongst HPV-positive participants. We will also evaluate associations between HPV type, cytology, VIA result, and histopathology results.

C. Subject Selection

Inclusion and Exclusion Criteria

Inclusion criteria for the study are:

- 1) ≥ 25 years of age
- 2) HIV-positive
- 3) Competent to understand study procedures and give informed consent.

Exclusion criteria are:

- 1) Currently pregnant (as diagnostic procedures for cervical cancer are often deferred during pregnancy)

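### The aims promise sensitivity and specificity of the whole two-stage algorithm; the planned calculation gives second-stage accuracy among HPV-positive women only

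*Combined protocol and SAP*

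**What the plan says.** Section B1 sets the target. Aim 1 is "To determine the sensitivity, specificity, and PPV of a two-stage screening algorithm that utilizes HPV testing followed by Pap smear", for high-grade dysplasia against colposcopy with histology. Aim 2 is the same with VIA as the second stage.

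Section B3.B, Sample Size, gives the purpose: "The goal of a two-stage algorithm is to increase PPV while maintaining sensitivity and specificity, and thus reduce overtreatment".

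Section B3.B, Data analysis, then restricts all three measures to women with a positive HPV test: "We will calculate sensitivity, specificity and PPV of HPV/Pap smear and HPV/VIA to detect high-grade cervical dysplasia amongst HPV-positive participants". No other section adds HPV-negative women to a denominator or rescales the result to all screened women.

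For the HPV test alone, section B2 gives the background figures: "HPV testing has a high sensitivity (93-100%) and specificity (80-90%), but low PPV (12-23%) for pre-invasive disease".

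Under Study Procedures (section B3.A), HPV-negative women do not go on to study VIA or routine colposcopy: "Participants who are HPV negative will only have the one study-related initial screening visit". For those with an abnormal smear the rule is: "If the Pap smear is abnormal, they will be referred to colposcopy per current Botswana Cervical Cancer guidelines".

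**The concern.** An algorithm that starts with an HPV test classes every HPV-negative woman as negative. Its specificity is therefore a proportion of all disease-free women screened, and most of them are HPV-negative. The planned calculation leaves those women out. It carries the names of the algorithms (HPV/Pap smear, HPV/VIA) but estimates how well the second test sorts women who have already tested positive.

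Within that group HPV testing alone has 100% sensitivity and 0% specificity by construction. The planned specificity therefore cannot show how far an algorithm improves on HPV testing alone in screened women. It is also on a different scale from the 80-90% HPV specificity in section B2.

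Read as the answer to the aims, the planned figures would make both algorithms look much less specific than they are in screened women, and possibly slightly more sensitive. The results are intended for national screening policy (sections B2 and B10), where the whole-population scale determines how many women are referred or treated unnecessarily.

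**Working it through.** **Plan's own figures.** Enrolment reproduces: 300 × 0.30 = 90 HPV-positive, and 90 × 0.90 = 81 returning. The power statement (over 80% for PPV 24% against 49%, two-sided alpha 0.05) names no test. Read as two independent groups of 81, power is 91.8%, which satisfies it. It concerns PPV only, and nothing below bears on it.

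**Inputs.**
- HPV positivity: 30% (B3.B, Sample Size), from 25 women; 15-45% (B2).
- HPV PPV: 24% (B3.B, Sample Size); 12-23% (B2).
- HPV sensitivity 93-100% and specificity 80-90% (B2).

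**Formula.** An algorithm false positive must first be HPV-positive, so

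whole-algorithm false-positive rate = f × conditional false-positive rate,

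where f = P(HPV-positive | disease-free) = prev × (1 − PPV) / (1 − prev × PPV / Se), with prev the HPV positivity and Se the HPV sensitivity. The conditional rate is 1/f times the whole-algorithm rate, whatever the accuracy of Pap or VIA.

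**Results.**

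| Inputs | f | Ratio 1/f |
|---|---|---|
| 30% positive, PPV 24%, Se 100% | 0.228/0.928 = 0.246 | 4.07 |
| 30% positive, PPV 24%, Se 93% | 0.228/0.9226 = 0.247 | 4.05 |
| 30% positive, PPV 12%, Se 93% | 0.264/0.9613 = 0.275 | 3.64 |
| 15% positive, PPV 24%, Se 100% | 0.114/0.964 = 0.118 | 8.46 |
| 45% positive, PPV 24%, Se 100% | 0.342/0.892 = 0.383 | 2.61 |
| 45% positive, PPV 12%, Se 93% | 0.396/0.9419 = 0.420 | 2.38 |
| HPV specificity 80% | 0.20 | 5 |
| HPV specificity 90% | 0.10 | 10 |

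HPV sensitivity hardly moves the ratio. HPV positivity and HPV specificity move it most.

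**In counts, on the planning figures.** Of 90 HPV-positive women, 90 × 0.24 = 21.6 have disease and 68.4 do not. With Se 100%, 300 − 21.6 = 278.4 of all women are disease-free; with Se 93%, 300 − 21.6/0.93 = 276.8. HPV testing alone has specificity 0% conditionally and 1 − 68.4/278.4 = 75.4% overall.

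**Illustration (assumed conditional specificities).** With f = 0.247, 80% becomes 1 − 0.247 × 0.20 = 95.1%, and 60% becomes 1 − 0.247 × 0.40 = 90.1%. A 20-point gap becomes about 5 points. Over ratios of 10 to 2.4 it becomes 20/10 = 2 to 20/2.4 = 8 points.

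**PPV and sensitivity.** Every algorithm positive is HPV-positive, so PPV is identical on both scales. Whole-algorithm sensitivity = conditional sensitivity × Se. An assumed conditional 70% becomes 65.1% at Se 93% and stays 70% at Se 100%. Se is common to both algorithms, so their ratio is unchanged.

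**Error from counting HPV-negative women as disease-free.** Take a poor second stage, with conditional specificity 8% (the lower VIA figure in B2). False positives are 68.4 × 0.92 = 62.9. The simple figure is 1 − 62.9/278.4 = 77.40%. The true figure is 1 − 62.9/276.8 = 77.26% at Se 93%, an error of 0.13 points before rounding. At an assumed Se of 80%, 300 − 21.6/0.80 = 273.0 are disease-free and the true figure is 76.95%, an error of 0.45 points.

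**Why to scale to all 90.** Suppose only the 81 returners are combined with the 210 HPV-negative women. There are 81 × 0.76 = 61.56 disease-free returners. At conditional specificity 60% the result is 1 − 24.62/271.56 = 90.9%, against 1 − 27.36/278.4 = 90.2% when scaled.

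**The case against.** The strongest reply is that the conditioning is already in the text: the analysis sentence names HPV-positive participants. The conditional figures are also useful. Conditional sensitivity is the share of HPV-detected disease that the second stage keeps, and conditional specificity is the share of HPV false positives it spares. A rule that needs both tests positive cannot be less specific than HPV testing alone, so the direction is known in advance. No section plans a comparison with the 80-90% background figure. PPV, the only quantity with a power statement, does not change.

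All of that stands, and it limits the consequence. It does not supply the specificity named in both aims, and knowing the direction does not give the size. The reply that a factor of four is too precise also stands: the 30% rests on 25 women and the 24% on one cited study, so the range has to be shown.

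Stronger readings are tempting but not supported:
- A reader might infer that the Pap-VIA comparison is biased. Both algorithms share the first stage, so ranking and relative sensitivity hold. Only the absolute specificity gap is rescaled.
- A reader might infer that disease found in HPV-negative women referred on an abnormal smear is lost to the study. The visible text does not describe its capture, but the study figure is not shown and the pilot protocol and consent pages are not available. The planned association analysis ("We will also evaluate associations between HPV type, cytology, VIA result, and histopathology results") is not limited to HPV-positive women. Few cases are in question: at HPV sensitivity 93% about 21.6/0.93 − 21.6 = 1.6 would be missed by the HPV test in 300 women. Section B5 describes referral for high-grade or persistent low-grade smears, so not every abnormal smear need lead to colposcopy. Nothing here rests on that reading.

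**Conclusion.** The mismatch is in the text. The aims name the whole algorithm; the analysis delivers second-stage accuracy given a positive HPV test. The conditional false-positive rate is about 4 times the whole-algorithm rate on the plan's own inputs, and about 2.4 to 10 times across the other figures in the document. The ratio exceeds 1 whenever some disease-free women test HPV-negative. The effect on sensitivity is small, a factor of 0.93 to 1.00, provided the literature range for HPV sensitivity applies to this population.

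The conditional figures are valid for what they measure. The fault is that they stand alone as the answer to aims on another scale. The change is worth making but does not threaten the study.

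**What to change.** In section B3.B, Data analysis:

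1. Keep the planned figures and label them, there and in reports, as second-stage accuracy among HPV-positive women.
2. Beside them report whole-algorithm specificity over all screened women, with HPV-negative women counted as algorithm-negative and disease-free. With N screened, n HPV-positive, m of these verified, and FP false positives and D diseased among the verified: specificity = 1 − (FP × n/m) / (N − (D × n/m)/Se). Se = 1 is the base case.
3. State the assumption behind n/m: women who return represent those who do not. Check it by clinic, since the Sample Size section itself expects follow-up to differ between the HIV and gynecology clinics.
4. Show the result over a range of assumed HPV sensitivity, for example 80% to 100%.
5. State that whole-algorithm sensitivity equals conditional sensitivity times HPV sensitivity, and that this study does not estimate the latter.

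No new visits, tests or participants are needed, because HPV results exist for all 300 women. The cost is a little extra analysis and two stated assumptions: that HPV-negative women are disease-free, and that returners are representative.
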